## Objectives

AIM #1. The primary objective of the study is to investigate the effect of levodopa on cardiovascular autonomic function in participants with PD (with and without OH) Participants with PD+OH and PD-OH will undergo autonomic testing of baroreflex cardiovagal and sympathetic noradrenergic functions on and off of levodopa on two separate days. The primary endpoint will be the change in systolic blood pressure from supine to tilt at 3 minutes. Results of autonomic testing on levodopa will be compared to testing off levodopa in all participants. Each patient will be his or her own control. Secondary endpoints will include validated indices of baroreflex cardiovagal and baroreflex sympathetic noradrenergic functions. Although levodopa may have a mild hypotensive effect, we hypothesize that levodopa will not induce or worsen the drop in blood pressure from supine to tilt at 3 minutes and will not worsen neurogenic orthostatic hypotension. Planned secondary endpoints will also investigate the differences in orthostatic vital signs with active standing and tilt table testing in patients with PD and the relationship between autonomic testing and the orthostatic symptom severity questionnaire.

**AIM #2.** Determine if levodopa has a different effect on cardiovascular autonomic function in participants with PD+OH compared to participants with PD-OH

The data from autonomic testing performed for AIM#1 will be used to assess AIM#2. The primary endpoint for AIM#2 will be indices of baroreflex cardiovagal and noradrenergic function. We hypothesize that levodopa will not alter baroreflex cardiovagal and sympathetic noradrenergic functions in either PD+OH or PD-OH.

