#### **Procedures:**

**Screening:** When the PI (or approved study personnel) makes contact with potential participant, basic information will be obtained to determine eligibility, including: medical history, PD diagnosis date and symptoms, current medications, among others.

Consent Process: Informed consent will be completed. Participants will complete the informed consent form on paper, or via REDCap. Participants will receive a paper copy per their request. Prior to signing the consent form, study personnel will thoroughly explain all study procedures and provide participants with ample time to ask any questions. The study team will continue to provide participants with opportunities to ask questions to ensure ongoing informed consent throughout the progress of the study.

Clinical assessment: The primary investigator will perform a medical history and physical examination before the testing procedures (baseline visit). The baseline visit will be performed on levodopa. The scales and assessments will include the Composite Autonomic Symptoms Score 31 (COMPASS 31), the Movement Disorder Society-Sponsored Revision of the Unified Parkinson's Disease Rating Scale (MDS-UPDRS) part I, II, III, and Hoehn and Yahr stage. The clinical assessment and scales are part of the standard of care in PD. Orthostatic vital signs (standing and supine measures of heart rate and blood pressure) will be performed during the baseline visit with active standing and the day of off-levodopa autonomic testing.

**Autonomic testing:** All participants will undergo autonomic testing on two separate days. The first autonomic testing will occur within 4 weeks of the baseline visit. The two autonomic tests will occur within a 2-week timeframe. To avoid any confounding of treatment effects and period effects, the order of testing (on versus off levodopa) will be randomized so testing on the first day will be on-levodopa for half of the participants and off-levodopa for the other participants. The procedures performed in this study are part of standardized clinical autonomic function testing. Autonomic testing will be performed by a research assistant with expertise in autonomic testing.

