Each participant will undergo testing in the on-levodopa state (45min to 1h after taking their regular dose of levodopa in the morning) and off-levodopa state. For testing in the off-state, the last dose of levodopa will be taken at least 12 hours before testing. Off-state in PD is expected to cause some degree of discomfort related to re-emergence / exacerbation of the motor and non-motor symptoms of PD. To limit the duration of the off-state, autonomic testing will be performed early in the morning between 7am and 8am. As soon as the autonomic testing is completed, the participant will be allowed to take levodopa. A participant may not be eligible for the study if the investigator believes that holding levodopa for testing is not safe. Briefly withholding levodopa, and/or medications that can interfere with heart rate or blood pressure measures, on the morning of the test is part of standard clinical autonomic function testing and is known to be well tolerated based on extensive clinical experience of the PI.

Participants will be instructed to have a standardized low-carbohydrate meal in the morning to avoid the confounding effects of postprandial hypotension and instructed to maintain a stable fluid intake to avoid volume shifts.

Autonomic testing will include non-invasive monitoring of blood pressure and heart rate during the Valsalva maneuver and during a 10-minutes head-up tilt.

*Electrocardiogram* (ECG): For monitoring the ECG, electrocardiographic leads are applied to the chest, abdomen, neck, or arms. All participants have ECG monitoring during the Valsalva maneuver and tilt table testing described below. Measurement of beat-to-beat heart rate part of standard clinical autonomic function testing.

Finger blood pressure measurement: A finger cuff is applied for non-invasive measurement of continuous blood pressure. All participants have finger blood pressure monitoring during the Valsalva maneuver and tilt table testing described below. Tracking blood pressure continuously via a finger cuff device is part of standard clinical autonomic function testing.

*Brachial blood pressure*: A clinical automated brachial cuff is applied for measurement of brachial blood pressure. All participants have brachial blood pressure monitoring before and during head-up tilt table testing. Measuring brachial blood pressure is part of standard clinical autonomic function testing.

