*Respiration*: A device for continuous monitoring of respiration is applied to the chest. All participants have respiratory monitoring during the experimental manipulations described below, unless technical limitations obviate such monitoring. Monitoring respiration is part of standard clinical autonomic function testing.

Valsalva maneuver: Assessment of beat-to-beat blood pressure and heart rate during and after performance of the Valsalva maneuver is a well-accepted standard autonomic function test. The participant lies supine on a tilt table with head on pillow. The participant blows or strains against a resistance for 12 seconds at 40 mmHg and then relaxes. If a "square wave" phenomenon is observed, the subject may be tilted at 20 degrees head up and the procedure repeated. At least 3 Valsalva maneuvers are done. The maneuvers are repeated (at least 1 minute between repetitions), until a technically adequate recording is obtained. Indices of

baroreflex-cardiovagal and cardiovascular noradrenergic functions are derived from the heart rate and blood pressure responses to the Valsalva maneuver. Indices of baroreflex cardiovagal function include the Valsalva ratio derived from the maximum heart rate generated by the Valsalva maneuver divided by the lowest heart rate occurring within 30 s of the peak heart rate and the slope of the relationship between cardiac R-R interval vs. systolic blood pressure in Phase II of the Valsalva maneuver is taken as a measure of baroreflex-cardiovagal gain (BRS-V). Indices of baroreflex cardiovascular noradrenergic function include the difference in BP between baseline and the end of Phase II, the pressure recovery time (PRT) which is the time from the nadir of the systolic blood pressure in Phase III of the Valsalva maneuver to complete return of systolic blood pressure to baseline, the adrenergic baroreflex sensitivity which is calculated from the slope of the line reflecting the difference of the baseline systolic blood pressure and the lowest systolic blood pressure in Phase III and the areas below the baseline systolic blood pressure calculated in Phase II (BRA-II) and IV (BRA-IV) of the Valsalva maneuver.

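### Valsalva indices are derived with levodopa state known and with no rule for judging or combining maneuvers, so a true ON–OFF difference could be attenuated

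*Combined protocol and SAP*

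**What the plan says.** All of the following is in the combined protocol and SAP.

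- **How the state is set (Procedures).** ON testing takes place "45min to 1h after taking their regular dose of levodopa in the morning". For OFF: "For testing in the off-state, the last dose of levodopa will be taken at least 12 hours before testing". No placebo is described, and the plan warns: "Off-state in PD is expected to cause some degree of discomfort related to re-emergence / exacerbation of the motor and non-motor symptoms of PD". Apart from the baseline visit, orthostatic vital signs are scheduled only on the OFF testing day, which is a further cue to state.
- **Who tests (Procedures).** "Autonomic testing will be performed by a research assistant with expertise in autonomic testing". No section mentions masking of the participant, the tester, the person who derives the indices, or the analyst.
- **Protection that is present (Procedures).** "the order of testing (on versus off levodopa) will be randomized". The reason given is to avoid confounding with period effects.
- **The maneuvers (Procedures, Valsalva maneuver).** "At least 3 Valsalva maneuvers are done", and "The maneuvers are repeated (at least 1 minute between repetitions), until a technically adequate recording is obtained". If a square-wave response appears, a repeat at 20 degrees head-up is optional.
- **Role of the indices (Objectives).** They are secondary endpoints for Aim 1 and the primary endpoint for Aim 2, where the expectation is: "We hypothesize that levodopa will not alter baroreflex cardiovagal and sympathetic noradrenergic functions in either PD+OH or PD-OH".

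**The concern.** Knowledge of levodopa state during the visit is unavoidable in this design and is not itself a fault. The difficulty comes one step later, when three or more recordings per session become one value per index. The plan does not say what makes a recording adequate, how many repeats are allowed, whether one maneuver is chosen or several are averaged, or whether both sessions must use the same position. It also does not define phase boundaries or the baseline window, on which most of the indices depend.

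These choices can be made by someone who knows the state and the study's hypothesis. Because that hypothesis is one of no change, expectation would tend to draw ON and OFF together, and the resulting lack of difference would look like confirmation. Neither the mixed model nor the Hochberg adjustment in the statistical section can detect or undo selection that happened before the data were entered.

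**Working it through.** **Plan's own figure.** There is none for these indices. The sample size of 40 is justified for ΔSBP-3' only, and this point does not depend on it.

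**Step 1. Where knowledge of state and discretion meet.**

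| Step | State known? | Rule in the plan |
|---|---|---|
| Deciding on another repeat | Yes, live | Adequacy, undefined; no maximum |
| Repeating at 20 degrees | Yes, live | Optional; no rule to match ON and OFF |
| Choosing or combining maneuvers | Not masked | None |
| Phase limits and baseline window | Not masked | None; no automated method named |
| Computing each index from its landmarks | Not masked | Defined for each index |

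Only the first two steps must happen at the bedside. The others can be done later from stored recordings.

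**Step 2. Which endpoints are exposed.**
- The Phase II slope (BRS-V), the end-of-Phase-II difference, pressure recovery time, adrenergic sensitivity, BRA-II and BRA-IV are exposed through maneuver choice and through the undefined phase limits or baseline.
- The Valsalva ratio is maximum heart rate over the lowest rate within 30 s of the peak. It needs no phase limit, so only maneuver choice exposes it.
- ΔSBP-3' is a pressure change at a fixed time during tilt, with no repeat-and-choose step described. It is much less exposed.

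**Step 3. Illustration of size.** None of these inputs comes from the documents. Assume three maneuvers per session, independent and normal with the same between-maneuver SD (set to 1), and a true ON–OFF difference D of 0.5, 1.0 or 1.5. Let r be the share of D that remains when selection is always applied, and w the share of participants in whom it occurs. Averaging all maneuvers retains all of D, so

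retained share = (1 − w) + w × r.

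Two forms of agreement-seeking choice were simulated with 400,000 replicates: (a) the ON maneuver closest to the OFF mean, and (b) the closest ON/OFF pair.

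| D | r, form (a) | Retained at w = 0.25 | r, form (b) | Retained at w = 0.25 |
|---|---|---|---|---|
| 0.5 | 0.35 | 0.75 + 0.25 × 0.35 = 0.84 | 0.11 | 0.75 + 0.25 × 0.11 = 0.78 |
| 1.0 | 0.42 | 0.75 + 0.25 × 0.42 = 0.855 | 0.15 | 0.75 + 0.25 × 0.15 = 0.79 |
| 1.5 | 0.51 | 0.75 + 0.25 × 0.51 = 0.88 | 0.21 | 0.75 + 0.25 × 0.21 = 0.80 |

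At w = 0.25 the range is therefore about 78–88%. At w = 0.10 it is about 91–95%, and at w = 1 it is 11–51%. When D = 0 both forms give a mean shift of zero, by symmetry.

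**The case against.** Several objections have force.

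- **The repeat rule governs acquisition.** It tells the tester when to stop and does not say that one maneuver is then picked. That is correct: selection is something the text leaves open, not something it prescribes.
- **Hand-marking of phases is not stated.** A reader might infer that someone places the phase limits by eye. The documents do not say so, and some landmarks are numerical: a 12-second strain at 40 mmHg, a pressure nadir, a return to baseline. What stands is that no rule or automated method is given.
- **Averaging alone removes the illustrated bias.** This is true of maneuver choice. It does not cover which recordings count as adequate or where phase limits fall. The gain from masking those steps has not been quantified.
- **Bedside decisions cannot be masked.** This stands. Coding the files does not reach live decisions on repeats or position.
- **The reach is limited.** The study's primary endpoint is largely outside the concern. The planned t tests of PD+OH against PD-OH use OFF data only, so masking levodopa state does not help there, although hiding group would.

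A reader might also be tempted to take the expected extreme of three normal draws, 0.85 SD, as the size of the bias. That describes always choosing an extreme in one fixed direction. It does not describe drift toward agreement, which gives no mean shift when there is no true effect.

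**Conclusion.** The concern holds as a cheap improvement. Followed as written, the plan lets a reader who knows levodopa state decide which recordings count and how they become an endpoint, and nothing later in the analysis can correct this. The consequence would be attenuation of a real ON–OFF difference in the Valsalva indices. The direction is credible because the hypothesis is one of no change.

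The bias is possible, not shown. The 78–88% figure rests wholly on the stated assumptions, including the 25% share, and the documents give nothing from which to compute the actual size. A reader might infer that a finding of no alteration would be uninterpretable. The documents do not support that: if there is truly no effect, agreement-seeking choice does not create a mean difference, and ΔSBP-3' is little affected. Unmasked testing is itself inferred from the design, since the plan does not use the term open-label.

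**What to change.** In the Valsalva part of Procedures:

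1. Leave live decisions on repeats, position and safety unmasked, but record every maneuver and the position in which it was done.
2. Export all recordings under a random code that hides levodopa state, visit and group.
3. Write down adequacy criteria and phase landmarks, including the baseline window, before any recording is read. Have existing staff apply them to the coded files.
4. Use the mean of all adequate maneuvers per session for each index.
5. Lock the indices before the code is linked to state.

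This needs no placebo, extra visit or larger sample. The costs are file handling, indices that are not final at the bedside, and a staff member other than the reader to hold the code list. The plan names REDCap only for consent, so where the list is kept has to be decided. The documents do not say who derives the indices; if the tester is also the reader, the code may mask only weakly. Two limits remain: live repeat decisions stay unmasked, and a trace may still hint at group.

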# Statistical Methods, Data Analysis and Interpretation

Summary statistics will be used to describe demographic and clinical variables. A sample size of 40 will achieve a power of 80% and a level of significance of 5%, for detecting a mean of 8 mmHg in ΔSBP-3' between the ON and OFF states with a within subject standard deviation of 20 mmHg based on published data on the effect of levodopa on supine and standing blood pressure in people with PD. The main statistical analysis will be conducted using mixed-effects regression models (linear mixed models), which will allow for the correlation of repeated measures within subjects. The response variable in our models will be ΔSBP-3', and the primary predictors will be the ON vs. OFF levodopa state and the period (visit 2 versus visit 3). A random intercept will be included for each subject to account for the within-subject correlation. For analyses of secondary outcomes, we will fit a mixed effect model and adjust the p value for multiple comparisons using the Hochberg multiple comparison procedure. Changes in blood pressure and heart rate with active standing and indices of baroreflex cardiovagal and sympathetic noradrenergic function OFF levodopa will be compared between PD+OH and PD-OH with Student t tests.

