## Sample Size:

At Utah:

All Centers: 40

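### The stated 80% power at N=40 does not follow from a within-subject SD of 20 mmHg; it needs a one-sided test and a different SD, and the plan states neither

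*Combined protocol and SAP*

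**What the plan says.** The section Statistical Methods, Data Analysis and Interpretation gives the only justification for the sample size: "A sample size of 40 will achieve a power of 80% and a level of significance of 5" per cent. The target is a mean ON-OFF difference of 8 mmHg in ΔSBP-3'. The calculation is made "with a within subject standard deviation of 20 mmHg based on published data". The Sample Size section confirms the number: "All Centers: 40".

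The design is a two-period crossover. Each participant is tested in both states, and under Procedures "the order of testing (on versus off levodopa) will be randomized". The primary analysis is a linear mixed model with levodopa state and period as predictors, and "A random intercept will be included for each subject to account for the within-subject correlation".

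On direction, the Objectives section says "we hypothesize that levodopa will not induce or worsen the drop in blood pressure from supine to tilt at 3 minutes". No section says whether the 5% level is one- or two-sided, or that 20 mmHg is the SD of the ON-OFF difference. No ON-OFF correlation is given.

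**The concern.** Power for a paired comparison depends on the SD of the within-person difference. The plan supplies something it calls a within-subject SD. In a random-intercept model with two measurements per person, that term means the residual SD of one measurement, and the difference between two measurements has an SD √2 times larger. Treating one as the other halves the apparent variance. The number of sides is a second open choice that also moves the answer.

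This matters because the study expects levodopa not to worsen the orthostatic fall, and the statistical section sets no margin. A non-significant result will tend to be read as supporting that expectation, so the probability of missing a real 8 mmHg effect is the risk of false reassurance. If sidedness stays open until analysis, the test performed may also differ from the one behind the power claim.

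**Working it through.** **Inputs**

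- N = 40 participants, each tested ON and OFF (Sample Size; Procedures).
- Difference to detect, δ = 8 mmHg in ΔSBP-3' (statistical section).
- α = 5%, sides not stated (statistical section).
- SD = 20 mmHg, labelled within-subject (statistical section).

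**Method.** Paired t-test power from the noncentral t distribution with 39 degrees of freedom:

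- standard error = SD_diff / √N
- noncentrality = δ / standard error
- power = probability that the noncentral t exceeds the critical value, which is 1.685 one-sided and 2.023 two-sided (adding the negligible opposite tail when two-sided)

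Using 38 degrees of freedom, to allow for the period term, changes each power by less than 0.1 percentage point.

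**Step 1: recover the plan's 80%.** Take 20 mmHg as the SD of the ON-OFF difference.

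- Standard error = 20/√40 = 3.162
- Noncentrality = 8/3.162 = 2.530
- One-sided power = 79.97%, which matches the plan
- Two-sided power = 69.4%, which does not

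**Step 2: use the SD as labelled.** With a within-subject SD of 20 mmHg, SD_diff = √(20² + 20²) = 20√2 = 28.28.

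- Standard error = 28.28/√40 = 4.472
- Noncentrality = 8/4.472 = 1.789
- One-sided power = 54.5%
- Two-sided power = 41.5%

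Neither test reaches 80%.

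**Step 3: size of the gap**

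| Meaning of 20 mmHg | Sides | Power at N=40 | Chance of missing 8 mmHg | Effect with 80% power at N=40 | N for 80% at 8 mmHg |
|---|---|---|---|---|---|
| SD of difference | 1 | 80.0% | 20% | 8.0 mmHg | 41 |
| SD of difference | 2 | 69.4% | 31% | 9.1 mmHg | 52 |
| Within-subject SD | 1 | 54.5% | 46% | 11.3 mmHg | 79 |
| Within-subject SD | 2 | 41.5% | 59% | 12.8 mmHg | 101 |

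Working backwards, 80% at N=40 needs SD_diff = 19.99 one-sided or 17.6 two-sided. Dividing by √2 gives a within-subject SD of about 14.1 or 12.5 mmHg, not 20.

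**Step 4: cross-checks**

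- The normal approximation gives 81.2% and 71.6% (one- and two-sided) for SD_diff = 20, and 55.7% and 43.2% for SD_diff = 28.28.
- A simulated two-period crossover with period adjustment gave 53.9% and 41.1% for a within-subject SD of 20, and 79.7% and 69.1% for 14.14.
- Other constructions also miss 80%: 80 observations as one sample gives 97% one-sided or 94% two-sided; unpaired 40 versus 40 gives 56% or 43%; unpaired 20 versus 20 gives 35% or 24%.

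**Step 5: a further reading, which needs an assumption.** If 20 mmHg were the total SD of a single ΔSBP-3' value with ON-OFF correlation ρ, then SD_diff = 20√(2(1−ρ)). Reaching 80% would need ρ of about 0.50 one-sided or 0.61 two-sided. The plan gives no correlation. For ρ from 0 to 0.8, power runs from 54.5% to 98.9% one-sided and from 41.5% to 97.4% two-sided.

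**The case against.** The best defence is that the 80% reproduces almost exactly, at 79.97%, under one coherent reading: one-sided 5% with 20 mmHg as the SD of the difference. That suggests, without proving it, how N=40 was obtained. In paired designs, within-subject SD is sometimes used loosely for the SD of within-person differences, and the power sentence comes before the model description and does not refer to it. The Objectives' hypothesis is directional, which is compatible with a one-sided test. On this view the fault is incomplete reporting, not a wrong sum. A per-measurement SD with a suitable correlation would be another route to 80%, and the source is published data on supine and standing pressures, so that reading is possible.

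Much of this is fair. The 54% and 41% figures hold for the SD as labelled, and the label may be loose. But each defence relies on something the plan does not say. A directional hypothesis does not declare a one-sided test. Even with the SD of the difference conceded, a two-sided 5% test gives 69%. The correlation route contradicts the label and needs a value that the plan does not supply.

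**Conclusion.** The concern holds. As written, the power claim does not follow from its inputs: with a within-subject SD of 20 mmHg, power for 8 mmHg at N=40 is 54% one-sided or 41% two-sided. If 20 mmHg is the SD of the ON-OFF difference, power is 80% one-sided or 69% two-sided. Among readings that need no assumed correlation, only the undeclared one-sided test with the relabelled SD supports the stated figure.

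These results assume complete data on all 40 participants and the standard meaning of within-subject SD in a random-intercept model. The source of the 20 mmHg is not shown, so the documents cannot say which of the four rows applies. The claim should be corrected before analysis because it is the plan's only justification for the sample size.

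**What to change.** Keep N=40. From the published source, state whether 20 mmHg is the SD of the ON-OFF difference or the residual within-subject SD. Declare the primary test one- or two-sided before analysis, and give the power that matches:

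- SD of the difference, one-sided: the 80% for 8 mmHg stands, provided both conditions are written down.
- SD of the difference, two-sided: about 69% for 8 mmHg, or 80% for 9.1 mmHg.
- Within-subject SD, one-sided: about 54% for 8 mmHg, or 80% for 11.3 mmHg.
- Within-subject SD, two-sided: about 41% for 8 mmHg, or 80% for 12.8 mmHg.

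If the source gives the SD of a single measurement instead, state the ON-OFF correlation assumed and compute the power from it.

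The cost is one sentence in the statistical section. No participants are added, and the endpoint and model stay as they are. The stated power may become less favourable.

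### No specified analysis estimates the levodopa effect on the 3-minute blood-pressure fall within PD+OH, although Aim 1 includes a hypothesis that only PD+OH can test

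*Combined protocol and SAP*

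**What the plan says.** **Endpoint and comparison.** Objectives, AIM #1: "The primary endpoint will be the change in systolic blood pressure from supine to tilt at 3 minutes". The ON/OFF comparison covers everyone: "Results of autonomic testing on levodopa will be compared to testing off levodopa in all participants". The stated objective names PD both with and without OH.

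**Hypothesis.** The same paragraph predicts that levodopa neither induces nor worsens the 3-minute fall, and adds that it "will not worsen neurogenic orthostatic hypotension".

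**Primary model.** Statistical Methods, Data Analysis and Interpretation takes ΔSBP-3' as the response and says "the primary predictors will be the ON vs. OFF levodopa state and the period (visit 2 versus visit 3", plus a random intercept per subject. It lists no OH-group term and no state-by-group term.

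**Analyses by group.** AIM #2 is to "Determine if levodopa has a different effect on cardiovascular autonomic function in participants with PD+OH compared to participants with PD-OH", but "The primary endpoint for AIM#2 will be indices of baroreflex cardiovagal and noradrenergic function". The only group comparison in the statistics section covers active-standing changes and baroreflex indices: "function OFF levodopa will be compared between PD+OH and PD-OH with Student t tests".

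**Secondary outcomes.** "For analyses of secondary outcomes, we will fit a mixed effect model and adjust the p value for multiple comparisons", by the Hochberg procedure. The terms of these models are not listed.

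**The concern.** Only a person who has nOH can have it worsened, so that clause of the hypothesis needs an ON-OFF estimate of ΔSBP-3' in PD+OH. The primary model returns one levodopa effect averaged over both groups. Its random intercept absorbs differences between subjects in the level of ΔSBP-3', but does not let the levodopa effect differ by group.

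This matters because the Background gives clinicians' reluctance to use levodopa in PD+OH as a reason for the study. The hypothesis predicts no effect, so a null pooled result could be read as reassurance about PD+OH when it is an average over a mix of participants whose proportions the plan does not state.

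**Working it through.** **1. Inputs.** From the statistics section: N = 40, 80% power, 5% significance (sidedness not stated), mean ON-OFF difference 8 mmHg, within-subject SD 20 mmHg. No split between PD+OH and PD-OH is given. I assume 20/20 as the illustration, with 12 and 26 PD+OH as a range (30% and 65% of 40, the nOH prevalence range in the Background). I also assume the same SD in both groups.

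**2. The plan's own figure.** For a paired difference, n = [SD × (z_α + z_0.80) / δ]².
- One-sided: [20 × (1.645 + 0.842)/8]² = 38.6, so 39. With the noncentral t, power at 40 is 80.0%. This reproduces the plan.
- Two-sided: [20 × (1.960 + 0.842)/8]² = 49.1, so 50 (52 with t). Power at 40 is 69%.
- If 20 is the SD at each visit, the SD of the difference is 20√2 = 28.3, and 78 (one-sided) or 99 (two-sided) are needed.

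The plan's 40 therefore fits 20 mmHg as the SD of the paired difference. I use that value below, with two-sided tests unless marked.

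**3. Where could a PD+OH estimate of the ON-OFF difference in ΔSBP-3' come from?**

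| Planned analysis | ΔSBP-3'? | ON vs OFF? | By OH group? |
|---|---|---|---|
| Primary mixed model | yes | yes | no |
| AIM #2 | not named; endpoint is baroreflex indices | yes | yes |
| Student t tests | no | no, OFF only | yes |
| Secondary mixed models | not stated | not stated | not stated |

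Study Procedures derives the baroreflex indices from the Valsalva maneuver, so ΔSBP-3' on tilt is not one of them. No row has all three features.

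**4. Dilution.** Let p be the PD+OH share, and δ₁ and δ₀ the levodopa effects in PD+OH and PD-OH.
- Pooled mean = pδ₁ + (1−p)δ₀.
- Pooled SD = √[400 + p(1−p)(δ₁−δ₀)²].
- Noncentrality = mean × √40 / SD, with 38 df.
- PD+OH alone: noncentrality = δ₁√n₁/20, with n₁−2 df.

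With δ₁ = 8 and a 20/20 split, PD+OH alone has noncentrality 8 × √20/20 = 1.79 and power 40% for every δ₀:

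| δ₀ (mmHg) | Pooled mean | Pooled SD | Noncentrality | Pooled power | PD+OH alone |
|---|---|---|---|---|---|
| 0 | 4.0 | √416 = 20.40 | 1.24 | 23% | 40% |
| 3 | 5.5 | √406.25 = 20.16 | 1.73 | 39% | 40% |
| 4 | 6.0 | √404 = 20.10 | 1.89 | 45% | 40% |
| 8 | 8.0 | 20.00 | 2.53 | 69% | 40% |

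One-sided, the first row is 34% pooled against 53% in PD+OH alone. With δ₀ = 0 and 12 or 26 PD+OH, the pooled mean is 0.30 × 8 = 2.4 or 0.65 × 8 = 5.2 mmHg. Pooled power is 11% or 35%, against 24% or 50% in PD+OH alone.

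**5. Precision of the added estimate.** Half-width of the 95% CI = t(0.975, n−2) × 20/√n.
- 12 PD+OH: 2.228 × 5.774 = 12.9 mmHg
- 20 PD+OH: 2.101 × 4.472 = 9.4 mmHg
- 26 PD+OH: 2.064 × 3.922 = 8.1 mmHg
- All 40, pooled: 2.024 × 3.162 = 6.4 mmHg

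If 20 is the per-visit SD, the half-width with 20 PD+OH is 9.4 × √2 = 13.3 mmHg.

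**6. State-by-group term.** With 20/20, SE = 20 × √(1/20 + 1/20) = 6.32 mmHg. For a group difference of 8 mmHg, 8/6.32 = 1.26, and power is about Φ(1.26 − 1.96) = 24%.

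**The case against.** **Pooling is the declared primary comparison.** The objective covers PD with and without OH. Inducing a fall is a question about PD-OH, and worsening the fall can apply to anyone. A reader might infer that the whole hypothesis concerns PD+OH, or that the pooled model is the wrong primary analysis. The documents support neither reading. This objection stands, and it limits the point to the nOH clause.

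**By-group analysis of ΔSBP-3' is not ruled out.** AIM #2 is worded broadly and reuses the AIM #1 data, which include the tilt, and the secondary models list no terms. It is therefore accurate to call the analysis unspecified, and too strong to call it excluded. Even so, the named Aim 2 endpoint and the only listed group test do not supply it, and an analysis chosen after seeing the data would be post hoc.

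**The power loss depends on the assumed PD-OH effect.** The documents allow a mild hypotensive effect without confining it to PD+OH. A reader might infer from the 23% that pooling generally hides harm. Step 4 shows that the comparison is about level at 3 mmHg in PD-OH and favours pooling at 4 mmHg or more. This objection also stands.

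**The subgroup estimate is imprecise.** This is true, but it is a reason to report the interval and limit the claim. It does not justify using the narrower pooled interval to answer a question about PD+OH.

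**Conclusion.** The point holds as a gap in specification. The pooled model answers the general part of the Aim 1 hypothesis, but no specified analysis estimates the ON-OFF difference in ΔSBP-3' in PD+OH, which the nOH clause requires. This conclusion rests on the text alone and on no numerical assumption.

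The size of any dilution does rest on assumptions: the split, equal SDs, 20 mmHg as the SD of the difference, and the PD-OH effect. In the unfavourable case (8 mmHg in PD+OH, none in PD-OH, 20/20) the pooled effect is halved to 4.0 mmHg and power is 23% against 40% in PD+OH alone. With a common 8 mmHg it is 69% against 40%. The case for change is the missing estimate, not a general gain in power.

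**What to change.** Keep the pooled model as the primary analysis. Add ΔSBP-3' to the endpoints examined by OH group, through a prespecified secondary mixed model with state, period, OH group, a state-by-group term and the random subject intercept. From that model, report the ON-OFF difference with 95% CI in PD+OH and in PD-OH, together with the interaction estimate, so that the groups are not compared by which one reaches significance. State that any conclusion about worsening of nOH rests on the PD+OH estimate and its interval, not on the pooled result alone.

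The cost is SAP wording. The data are already collected, and no extra visits or participants are needed. The limitation is precision: half-widths of about 8.1 to 12.9 mmHg for 26 down to 12 PD+OH exceed the 8 mmHg target, and the interaction test has about 24% power at 20/20. The plan should therefore describe the by-group result as estimation, and not treat a non-significant PD+OH difference or interaction as proof of no harm.
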